### 18.3.1. LABORATORY REFERENCE RANGES AND MARKEDLY ABNORMAL CRITERIA

Quantitative laboratory measurements will be compared with the relevant laboratory reference ranges in SI units and categorized as:

• Low: Below the lower limit of the laboratory reference range.

- Normal: Within the laboratory reference range (upper and lower limit included).
- High: Above the upper limit of the laboratory reference range.
- Treatment-emergent high result: a change from a value less than or equal to the high limit at all baseline visits to a value greater than the high limit at any time during the treatment period.
- Treatment-emergent low result: a change from a value greater than or equal to the low limit at all baseline visits to a value less than the low limit at any time during the treament period.

### 18.4. 12-LEAD ECG

Results from the central 12-lead ECG Reading Centre will be included in the reporting of this study. The ECGs will be read and interpreted by the central ECG laboratory. At all scheduled visits, ECGs were collected once per visit, prior to administration of the first daily dose of study treatment.

The following ECG parameters will be reported for this study on the central read for each safety ECG:

- PR Interval (msec)
- QRS Interval (msec)
- QT Interval (msec)
- QTcF Interval (msec) [derived]
- QTcB Interval (msec) [derived, optional]
- Heart Rate (HR) (bpm)
- Overall interpretation of ECG (Investigator's judgment):
  - Normal
  - Abnormal, Not Clinically Significant (Abnormal NCS)
  - Abnormal, Clinically Significant (Abnormal CS)

The following summaries will be provided by treatment group for ECG data:

• Value by visit (for quantitative measurements)

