#### 8.3.4.6. Electrocardiography

The change from Baseline Descriptive statistics for each of the ECG parameters will be presented by treatment group. The incidence of outlier ECG results will be tabulated. Individual ECG values will be listed by visit and summarized using descriptive statistics. Parameters to be provided on the confirmed read for each safety ECG are HR and the following intervals: RR, PR, QRS, QT, and QTc (QTcF required, QTcB optional). The ECGs will be read and interpreted by the central ECG laboratory. Post-Baseline ECGs for each subject will be compared with the Baseline ECG. Any clinically significant change from Baseline may be recorded as an AE if deemed appropriate by the Investigator, or Investigator in consultation with the Medical Monitor. Outlier analysis will be performed on all subjects with QTcF values greater than 500 ms or change from Baseline > 60 ms in the absence of Baseline ECG abnormalities that preclude accurate surface ECG assessment of ventricular repolarization (eg, bundle branch block).

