#### 8.3.5. Other Analyses

#### 8.3.6. Statistical Analyses for the Long-Term Extension

The LTE has 2 treatment groups, 25 mg and 50 mg. Based on subjects' treatment assignments in the Main Study and the LTE study, subjects can be classified into 6 unique treatment groups: "Placebo|25 mg", "Placebo|50 mg", "10 mg|25 mg", "10 mg|50 mg", "25 mg|25 mg", and "50 mg|50 mg".

Safety analyses will be performed as described above for the Main Study. In addition, new AEs that occur after the first dose in the LTE or TEAEs which occurred in the Main Study period and increase in severity after the first dose of LTE study treatment will also be summarized by the 6 unique treatment groups. Exposure will also be summarized by unique treatment group.

A descriptive summary of observed plasma concentrations will be provided by treatment group.

Summary statistics will be provided for efficacy endpoints by unique treatment group. Proportion-based endpoints including responders will be summarized with frequency count and percentage. Continuous endpoints will be summarized with descriptive statistics including mean, median, standard deviation, minimum, and maximum values. There is no formal between-treatment comparison for efficacy endpoints.

Additional analyses may be performed in some subgroups of medical interest, such as sex, age, race, and IBS subtype. Details of the analyses will be provided in the SAP for LTE.

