#### 4.3. CHANGES TO ANALYSIS FROM PROTOCOL

After completing the analysis for the Main Study Period, the decision was made to terminate the study early and end the LTE for all subjects. Analyses for the LTE will reflect all data collected until the study is terminated. Population PK endpoints, Ctrough of olorinab and its primary metabolites, will not be included in this SAP. Removal of PK exhibits (TFLs) was agreed upon on 01APR2021.

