### 18.3. LABORATORY EVALUATIONS

Results from the central laboratory will be included in the reporting of this study for chemistry, hematology, coagulation, urinalysis, thyroid chemistry, celiac, and virology. pregnancy. A list of laboratory assessments to be included in the outputs is included in Table 3 in the protocol. If local and central laboratory assessments are available from the same day, central laboratory assessments will be used in the analysis.

Presentations will use SI Units. Quantitative laboratory measurements reported as "< X", i.e. below the lower limit of quantification (BLQ), or "> X", i.e. above the upper limit of quantification (ULQ), will be converted to X for the purpose of quantitative summaries, but will be presented as recorded, i.e. as "< X" or "> X" in the listings.

Laboratory parameters such as hepatic enzymes, renal function and hematology values will be grouped and presented together. The following summaries will be provided for laboratory data:

- Value and change from LTE baseline by visit (for quantitative measurements)
- Incidence of abnormal values according to laboratory reference ranges by visit
- Shift from LTE baseline to end of treatment according to laboratory reference range (for quantitative measurements and categorical measurements)
- Summary of subjects with treatment-emergent abnormal lab results
- Listing of subject's laboratory assessments at all timepoints. Values outside of the central laboratory reference range will be flagged. Values obtained from local laboratory will be flagged.

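### The LTE SAP reduces the ECG analysis to values by visit, dropping the protocol's change-from-baseline and QTcF outlier tables without declaring it

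*SAP*

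**What the plan says.** Protocol 8.3.6 says of the LTE: "Safety analyses will be performed as described above for the Main Study". The ECG methods it points back to are in Protocol 8.3.4.6. They include descriptive change from Baseline by treatment group, and two statements on outliers: "The incidence of outlier ECG results will be tabulated" and "Outlier analysis will be performed on all subjects with QTcF values greater than 500 ms or change from Baseline > 60 ms". The QTcF analysis is qualified to exclude Baseline abnormalities that prevent a reliable reading. The synopsis also lists ECG change from Baseline and outlier tabulation among the safety analyses.

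LTE SAP 18.4 confirms that the data exist: "At all scheduled visits, ECGs were collected once per visit, prior to administration of the first daily dose of study treatment". Its list of planned ECG summaries has one entry, "Value by visit (for quantitative measurements", and the text then moves on to vital signs. Main Study SAP 19.4.1, on outliers and morphology, has no LTE counterpart.

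LTE SAP 4.3 reports that, after the Main Study analysis, "the decision was made to terminate the study early and end the LTE for all subjects". It also reports one dropped set of outputs: "Removal of PK exhibits (TFLs) was agreed upon on 01APR2021". ECG is not mentioned.

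For laboratory data, LTE SAP 18.3 plans "Value and change from LTE baseline by visit (for quantitative measurements". LTE SAP 18.5 likewise plans change from LTE baseline for vital signs, with counts of potentially clinically significant (PCS) values.

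**The concern.** Long-term safety and tolerability is the LTE's only primary objective. A table of raw ECG values by visit mixes differences between subjects with changes within them, and it does not count threshold crossings. Change from LTE baseline is the within-subject measure of what happens after dosing starts. It is relevant to all six treatment sequences: placebo and 10 mg subjects move to 25 or 50 mg, and subjects staying on 25 or 50 mg restart after at least about two weeks off drug (Protocol 3.8).

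The LTE SAP was finalised after the Main Study had been analysed. A safety analysis narrower than the protocol's, written at that stage, needs a stated reason. The SAP has a section for such reasons and used it for PK only.

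**Working it through.** No sample-size or error-rate figure is involved, so the check is a comparison of texts with simple counts.

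**Step 1. ECG elements, protocol against the two SAPs.**

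| Element in Protocol 8.3.4.6 | Main Study SAP 19.4 and 19.4.1 | LTE SAP 18.4 | Declared in LTE SAP 4.3 |
|---|---|---|---|
| Descriptive values by visit | Yes | Yes | Not needed |
| Change from Baseline by treatment | Yes | No | No |
| Outlier incidence tabulated | Yes, 23 rows | No | No |
| QTcF above 500 ms or change above 60 ms | Yes, among 4 QTcF rows | No | No |

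The Main Study SAP plans 3 types of ECG summary plus 23 outlier and morphology rows. The LTE SAP plans 1 type and 0 rows. Three of the four protocol elements in the table are absent and undeclared.

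**Step 2. Does early termination explain it?** LTE SAP 4.3 says the analyses will use everything collected up to termination. Change from LTE baseline survives for laboratory data and vital signs under the same termination. LTE SAP 7.2 gives a general baseline definition that would serve for ECG. Termination therefore does not account for the ECG gap.

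**Step 3. What remains visible?** LTE SAP 18 says safety data are listed as well as summarised. Protocol 8.3 summarises continuous variables with minimum and maximum. A QTcF above 500 ms in the record chosen for a visit would therefore show as that visit's maximum in its treatment group, and in the listing. A change above 60 ms would have to be worked out from the listing, subject by subject. Neither route gives an incidence by treatment.

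**Step 4. Related wording in the Main Study SAP (minor).**

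- *ECG.* Section 7.3 keeps the earliest ECG of a day, and 19.4 summarises value and change by visit. Timed post-dose ECGs in 19.4 number 1 after Amendment 2 (Day 1, 2 h). Before it there were 4 on Day 1 (2, 4, 8, 10 h) plus 2 on Day 2 (2, 4 h), so 6. If the rule runs over the whole day, the pre-dose reading is kept and 0 of 1 and 0 of 6 enter the value and change summaries. If it runs only over post-baseline records, since 7.2 separates baseline by date and time, 1 of 1 and 1 of 6 enter.
- *Orthostatic vital signs, subjects enrolled before Amendment 2.* Section 19.5 selects the earliest Day 1 and Day 2 reading, then asks for values per visit or timepoint. With 5 readings on Day 1 and 3 on Day 2, the first instruction uses 2 of 8 and the second 8 of 8. A post-dose change of X on Day 1 appears as 0 under one and X under the other.

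**The case against.** The strongest defence is that little would be learned. ECG is not named in the LTE primary endpoint, every LTE subject receives olorinab, and no between-treatment safety comparison is planned. Protocol 1.2 reports no notable ECG change apart from heart rate in the single-dose study. Each re-randomised sequence could hold at most about 60 / 2 = 30 subjects even if a whole Main Study arm entered, and the extension stopped early. An outlier table may well be empty. All of this stands, and it limits the weight of the point. It does not remove the protocol requirement, and an empty table would itself be a safety result.

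The LTE table shells and Appendix 1 are not available and could contain more. But section 18.4 enumerates its summaries, and shells would not supply the missing declaration in 4.3.

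A reader might infer four stronger things that the documents do not support:

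- *That LTE QTcF outliers surface only if an investigator reports an adverse event.* Listings and visit maxima are other routes (Step 3).
- *That the cut was made because of something seen in the Main Study.* The documents give the order of events and no reason for the ECG change.
- *That Main Study post-dose ECGs are excluded from safety assessment.* Section 7.3 keeps all measurements for abnormality and worst-case summaries, so they reach the outlier table. The same-day rule also sits in a section on retests and unscheduled data, the window table is not visible, and the protocol does not ask for means by timepoint.
- *That the same-day average in 7.3 is a further competing rule for orthostatic readings, with a blood-pressure effect at stake.* Section 19.5 is specific to these readings and can be read as overriding 7.3. PCS counts cover the post-dose period. The 6 h blood-pressure low in Protocol 1.2 was at 100 and 200 mg. The lowest group, 50 mg (Protocol 3.3.1) and this trial's top dose, was generally similar to placebo on Day 1.

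**Conclusion.** The point holds for the LTE ECG analysis and should be fixed. LTE SAP 18.4 omits three ECG elements that Protocol 8.3.6 and 8.3.4.6 require, and LTE SAP 4.3 does not declare it. The loss is within-subject change and outlier incidence by treatment; individual extreme values are not lost. The conclusion rests on the printed SAP text being the full list of planned LTE ECG summaries, and on ECGs having been collected as 18.4 states (the schedule of assessments is not visible). It does not touch the Main Study efficacy results.

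The two Main Study items are clarifications of wording. The ECG item is a probable reading that cannot be settled without the window table. The orthostatic item is one inconsistency within 19.5, limited to an early cohort of unstated size.

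**What to change.** **LTE SAP 18.4.** Add ECG change from LTE baseline by visit, by treatment, and a tabulation by treatment of subjects with QTcF above 500 ms and with change above 60 ms, keeping the protocol's qualifier on Baseline abnormalities. If the sponsor prefers not to, state the omission and the reason in 4.3.

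**Minor, Main Study SAP 7.3 and 19.4.** Limit the earliest-of-day ECG rule to repeats at the same nominal timepoint, so that the Day 1 2 h reading appears in the value and change summaries.

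**Minor, Main Study SAP 19.5.** Reconcile the two instructions by summarising orthostatic readings by nominal timepoint for the pre-Amendment 2 cohort, labelled as such. Note that PCS counts already include post-dose readings.

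**Cost.** A few tables from collected data and some SAP wording, with no new assessments. The LTE tables will be small, incomplete because of early termination, and likely to show few or no outliers.

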## 18.5. VITAL SIGNS

Orthostatic vital signs (VS) include the collection of blood pressure (BP) and HR after the subject has been resting in the supine position for at least 5 minutes and then again after 1 and 3 minutes of standing. For gap subjects, orthostatic VS were collected at the screening and for continuing subjects, orthostatic VS were collected at the main study Week 14 visit. Screening orthostatic vital signs will be included in data listings of vital signs.

For all other visits, supine vital signs were collected once per visit, prior to administration of the first daily dose of study treatment.

Baseline VS is defined as the supine VS collected prior to or on the date of the administration of the first daily dose of LTE study treatment on Day 1.

The following VS data will be summarized using descriptive statistics by treatment group as denoted in the Presentation of Treatment Groups in Appendix 1.

- The actual measurement values of vital signs at each visit/timepoint
- Change from LTE baseline: calculated as post-baseline values minus the VS baseline value.

Body temperature and respiratory rate were collected once per visit, prior to the administration of the first daily dose of study treatment (for visits occurring during the Treatment Period).

Vital sign values meeting the criteria as defined in

Table 2 below will be categorized as potentially clinically significant (PCS) findings. These findings will be summarized with frequency count and percentage for each treatment as well as for the active treatments pooled, both overall and by scheduled visit. The summaries and counts will be presented at both the subject level (counting subjects with PCS findings) and event level (counting all PCS events).

**PCS Parameter** Category **PCS** Criteria Systolic BP (mm Hg)  $\geq$  140 Supine and Supine increase from baseline  $\geq$  20 High Low  $\leq$  90 Supine and Supine decrease from baseline  $\geq$  20 Diastolic BP (mm Hg) High  $\geq$  90 Supine and Supine increase from baseline  $\geq$  15 < 40 Supine and Supine decrease from baseline ≥ 15 Low Pulse Rate (bpm) High ≥ 100 Supine < 40 Supine Low High  $\geq 28$ Respiratory Rate (brpm) Low ≤8 > 38 High Temperature (°C) < 35 Low

Table 2: Vital Sign PCS Criteria

Abbreviation: bpm = beats per minute; BP = blood pressure; brpm = breaths per minute; PCS = potentially clinically significant

#### 18.5.1. VITAL SIGNS SPECIFIC DERIVATIONS

• Temperature ( ${}^{0}$ C) = (5/9) (Temperature ( ${}^{0}$ F) – 32)

## 18.6. PHYSICAL EXAMINATION

All physical examination assessments will be listed.

### 19. PHARMACOKINETICS ANALYSIS

Pharmacokinetic analyses may be completed by Sponsor and will be described in a separate analysis plan if needed.

### 20. IMPACT OF COVID-19

The study has been closely monitored during the period of COVID-19 and the impact of COVID-19 on data analyses is minimal. The below analyses related to COVID-19 are planned to document any impacts of the pandemic. Post hoc exploratory data analyses may be planned after database lock if the data warrants the request.

- Summary of major protocol deviations caused by COVID-19
- A listing of any adverse events related to COVID-19
- A listing of any subjects with phone or remote visits due to COVID-19.

### 21. GENETIC AND BIOMARKER ANALYSES

Genetic and biomarker analyses will be completed by Sponsor and will be described in a separate analysis plan if needed.

## 22. DATA NOT SUMMARIZED OR PRESENTED

The other variables and/or domains not summarized or presented are:

- Comments
- Meals (Day 1)

These domains and/or variables will not be summarized or presented but will be available in the clinical study database, SDTM and/or ADaM datasets.

# 25. APPENDIX 2. PARTIAL DATE CONVENTIONS

Imputed dates will NOT be presented in the listings.

# **ALGORITHM FOR TREATMENT EMERGENCE OF ADVERSE EVENTS:**

AE START	AE STOP	ACTION
DATE	DATE	
Known	Known,	If AE start date < study treatment first LTE dose date,
	Partial or	then not TEAE
	Missing	If AE start date $\geq$ study treatment first LTE dose date,
		then TEAE
Partial, but	Known,	Not TEAE
known	Partial or	
components	Missing	
show that it		
cannot be on or		
after date of		
first dose of		
study treatment		
Partial, could be	Known	If AE stop date < study treatment first LTE dose date,
on or after date		then not TEAE
of first dose of		If AE stop date ≥ study treatment first LTE dose date,
study treatment		then TEAE
	Partial	Impute AE stop date as latest possible date (i.e. last
		day of month if day unknown or 31st December if
		day and month are unknown), then:
		If AE stop date < study treatment first LTE dose date,
		then not TEAE
		If AE stop date ≥ study treatment first LTE dose date,
		then TEAE
	Missing	Assumed TEAE

Page 45 of 50

AE START	AE STOP	ACTION
DATE	DATE	
Missing	Known	If AE stop date < study treatment first LTE dose date, then not TEAE  If AE stop date ≥ study treatment first LTE dose date, then TEAE
	Partial	Impute AE stop date as latest possible date (i.e. last day of month if day unknown or 31st December if day and month are unknown), then:  If AE stop date < study treatment first LTE dose date, then not TEAE  If AE stop date ≥ study treatment first LTE dose date, then TEAE
	Missing	Assumed TEAE

# **ALGORITHM FOR PRIOR / CONCOMITANT MEDICATIONS:**

START	STOP	ACTION
DATE	DATE	
Known	Known	If medication stop date < study treatment first LTE dose date, assign as prior  If medication stop date ≥ study treatment first LTE dose date, assign as concomitant
	Partial	Impute stop date as latest possible date (i.e. last day of month if day unknown or 31st December if day and month are unknown), then:  If medication stop date < study treatment first LTE dose date, assign as prior  If medication stop date ≥ study treatment first LTE dose date, assign as concomitant
	Missing	If medication stop date is missing could never be assumed a prior medication, assign as concomitant

Page 46 of 50

[figure not shown]
START DATE	STOP DATE	ACTION
DAIL	DATE	
Partial	Known	Impute start date as earliest possible date (i.e. first day of month if day unknown or 1st January if day and month are unknown), then:  If medication stop date < study treatment first LTE dose date, assign as prior  If medication stop date ≥ study treatment first LTE dose date, assign as concomitant
	Partial	Impute start date as earliest possible date (i.e. first day of month if day unknown or 1st January if day and month are unknown) and impute stop date as latest possible date (i.e. last day of month if day unknown or 31st December if day and month are unknown), then:  If medication stop date < study treatment first LTE dose date, assign as prior  If medication stop date ≥ study treatment first LTE dose date, assign as concomitant
	Missing	Impute start date as earliest possible date (i.e. first day of month if day unknown or 1st January if day and month are unknown), then:  If medication stop date is missing could never be assumed a prior medication, assign as concomitant
Missing	Known	If medication stop date < study treatment first LTE dose date, assign as prior Else assign as concomitant

Page 47 of 50

START	STOP	ACTION
DATE	DATE	
	Partial	Impute stop date as latest possible date (i.e. last day of month if day unknown or 31st December if day and month are unknown), then:  If medication stop date < study treatment first LTE dose date, assign as prior  If medication stop date ≥ study treatment first LTE dose date, assign as concomitant
	Missing	Assign as concomitant

Page 48 of 50

Page 49 of 50

Page 50 of 50

